STUDY PROTOCOL AND STATISTICAL ANALYSIS PLAN

Effectiveness and Safety of Single-port Versus Multi-port Laparoscopic Surgery in the Treatment of Ectopic Pregnancy

Protocol identification number 5863/QD-BVHV (dated April, 2023)

Table of contents

1. Introduction	3
2. Study design	3-5
3. Aims and objectives	5
4. Outcomes	5
5. Populations and subgroups to be analyzed	6
6. Analyses	6
7. References	6

1. Introduction

Single-port laparoscopic surgery has become one of the treatment options for ectopic pregnancy with certain advantages such as reduced numbers of incision and scars, fast recovery, and increased patient's satisfaction post-surgery. Although several research groups have investigated the differences between single-port and traditional multi-port laparoscopic surgery, the investigators have not had such studies carried out at Hung Vuong hospital. Therefore, the investigators set out this project to compare the effectiveness and safety of single-port versus conventional multi-port laparoscopic surgery in the treatment of ectopic pregnancy at Hung Vuong hospital, aiming to gain insights into the application potential of this technique to the gynecologic laparoscopy procedures.

2. Study design

Study subjects will be recruited from November 2023 to May 2024 at Hung Vuong hospital, Ho Chi Minh city, Vietnam. Inclusion criteria for participants in this study include pregnant women who are 18 years old or older; who are indicated for laparoscopic surgery to treat ectopic pregnancy; and who agree to participate and provide a consent. Exclusion criteria include pregnant women who are allergic to anesthesia; who have hemodynamic instability; or who have ruptured ectopic pregnancies. The study is a parallel-group randomized control trial with 2 arms and no blinding. Arm 1 includes patients who will undergo single-port laparoscopy while aim 2 have patients undergo multi-port laparoscopy. All patients are randomized using computer-generated sequences with allocation ratio 1:1. Primary outcomes include blood loss, and surgical time. Secondary outcomes include pain intensity, surgical complications, hospital stay, and pneumoperitoneum. Blood loss and surgical time will be measured right after surgery while other outcomes will be measured during hospital stay. Technically, the investigators will perform examination 3-4 days post-surgery. Sampling will be stopped and the study will be concluded when patients are discharged from the hospital. The study design is visualized in Figure 1 below.

[figure not shown]

Figure 1: The CONSORT flow diagram of the study

Sample size calculation

The sample size is calculated based on the following formula:

$$n = \frac{(z_{1-\frac{\alpha}{2}} + z_{1-\beta})^2 [\sigma_1^2 + \frac{\sigma_2^2}{r}]}{\Delta^2}$$

$$r = \frac{n_1}{n_2}$$

$$\Delta = \mu_1 - \mu_2$$

Where:

n: required minimum sample size in each group

μ : outcome in each group

σ : standard deviation in each group

z: z score

α : type I error, $\alpha = 0,05$

β : type II error, $\beta = 0,15$ (statistical power = 0,85)

Based on Hsu-Dong Sun's group [1], sample sizes for each variable are as follows

Variables	4-port	1-port	Sample size
Bowel recovery time	$6,2 \pm 1$	$7,2 \pm 1,4$	24
Blood loss	$125 \pm 156,9$	335 ± 104	50
Visual analogue scale	$3 \pm 0,5$	$3,6 \pm 0,6$	14

The investigators anticipate to obtain the sample size of 50 for each group.

3. Aims and objectives

The aim is to compare the effectiveness and safety of single-port versus traditional multi-port laparoscopic surgery in the treatment of ectopic pregnancy. Specifically, the surgical effectiveness will be evaluated via beta-hCG values, ultrasound imaging, and rate of switching to open surgery. The surgical safety will be evaluated via surgical time, blood loss, pain intensity, and surgical complications.

4. Outcomes

The primary outcomes of interest are the amount of blood loss during surgery, and surgical time. Secondary outcomes include pain intensity as indicated by visual analogue scale, surgical complications such as organ damages and surgical site infections, hospital stay, and pneumoperitoneum. The primary outcomes will be evaluated immediately post-surgery while the secondary outcomes will be evaluated within 4 weeks post-surgery by qualified practitioners.

5. Populations and subgroups to be analyzed

Populations: intention-to-treat

Subgroups: single-port versus multi-port group. These 2 subgroups will be analyzed using intention-to-treat populations.

6. Analyses

Data will be analyzed using Stata 16 (StataCorp LLC, College Station, TX). Normally distributed data will be expressed as mean \pm standard deviation, while non-normally distributed data will be shown as medians with interquartile ranges. T-test for normally distributed continuous variables and Mann-Whitney-U test for non-normally distributed continuous variables will be used to compare between groups. Categorical variables will be reported as absolute numbers and percentages; the Chi-square test or Fisher's exact test will be utilized for comparison. A *p*-value of <0.05 will be considered statistically significant.

7. References

- [1] Sun, Hsu-Dong, et al. "Comparison of single-port and three-port laparoscopic salpingectomy in the management for tubal pregnancy." *Journal of the Chinese Medical Association* 81.5 (2018): 469-474.

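### Surgical time is a primary outcome with no sizing assumptions, and the plan has no success rule for its two primary outcomes, so neither the 85% power nor the 5% error is established across them

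*Combined protocol and SAP*

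**What the plan says.** Section 2 (Study design) names two primary outcomes: "Primary outcomes include blood loss, and surgical time". Section 4 (Outcomes) repeats them: "The primary outcomes of interest are the amount of blood loss during surgery, and surgical time". Neither section ranks them.

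The secondary outcomes in Section 2 are given as "Secondary outcomes include pain intensity, surgical complications, hospital stay, and pneumoperitoneum". Section 4 has the same list, specifying the visual analogue scale for pain and continuing with "surgical complications such as organ damages and surgical site infections, hospital stay, and pneumoperitoneum".

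The sample-size calculation in Section 2 uses a two-sided normal formula for two means with alpha 0.05 and "statistical power = 0,85". Its table has three rows:

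- "Bowel recovery time", n = 24
- blood loss, n = 50
- visual analogue scale, n = 14

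The planned size is 50 per group, equal to the largest row.

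Section 6 (Analyses) names the tests and sets one threshold, p below 0.05. It gives no order of testing, no adjustment, and no statement of what counts as a positive trial.

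**The concern.** The table and the outcome lists do not match. Blood loss is in both. Surgical time is primary but has no row, and no mean, SD or target difference for it appears anywhere in the document. Bowel recovery time has a row but is not a primary or secondary outcome, and it is not among the effectiveness and safety measures in Section 3.

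Two things are at stake. First, a non-significant result on surgical time would be hard to interpret, because nobody has stated what difference the trial could detect. Second, with two primaries each tested at 5% and no success rule, the trial could be called positive on whichever one reaches significance. The overall false-positive rate would then exceed the alpha used to size it.

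**Working it through.** **Inputs from the document.** Alpha 0.05 two-sided, power 0.85, 1:1 allocation, 50 per group. Blood loss: 125 ± 156.9 (4-port) against 335 ± 104 (1-port). Bowel recovery time: 6.2 ± 1 against 7.2 ± 1.4. Visual analogue scale: 3 ± 0.5 against 3.6 ± 0.6. For surgical time there are no inputs.

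**1. The plan's own figures.** With r = 1 the formula is n = (z₀.₉₇₅ + z₀.₈₅)² (σ₁² + σ₂²)/Δ², and (1.960 + 1.036)² = 8.978.

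- Blood loss: 8.978 × (24,617.6 + 10,816)/210² = 8.978 × 35,433.6/44,100 = 7.2, so 8 per group. The table says 50.
- Bowel recovery time: 8.978 × (1 + 1.96)/1² = 26.6, so 27. The table says 24.
- Visual analogue scale: 8.978 × (0.25 + 0.36)/0.6² = 15.2, so 16. The table says 14.

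At 80% power the multiplier is 7.849. The last two rows then come out at exactly 24 and 14, but blood loss gives 7. Across one- and two-sided tests and power from 80% to 95%, blood loss needs 5 to 11 per group (10 to 22 in total), never 50. With the printed SDs, n = 50 corresponds to a difference of √(8.978 × 35,433.6/50) ≈ 80, not 210. At the printed difference, power with 50 per group exceeds 99.9%.

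**2. What 50 per group gives for surgical time.** No n can be derived, so the result is in SD units. The detectable difference is (z₁₋α/₂ + z₀.₈₅) × √(2/50).

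- Alpha 5%: (1.960 + 1.036) × 0.2 = 0.60 SD (0.61 t-based).
- Alpha 2.5%: (2.241 + 1.036) × 0.2 = 0.66 SD.

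Over assumed true differences at two-sided 5% (normal approximation):

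| Difference (SD) | Power at 50 per group | n per group for 85% power |
|---|---|---|
| 0.3 | 32% | 200 |
| 0.4 | 52% | 113 |
| 0.5 | 71% | 72 |
| 0.6 | 85% | 50 |
| 0.8 | 98% | 29 |

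**3. Error across the two primaries.** Assume no true effect on either outcome and each tested at two-sided 5%. The correlations are assumptions, since the document gives none; the non-zero cases use a bivariate normal.

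| Correlation of the test statistics | At least one significant | Both significant |
|---|---|---|
| 0 | 1 − 0.95² = 9.75% | 0.05² = 0.25% |
| 0.5 | 9.1% | 0.9% |
| 0.7 | 8.3% | 1.7% |

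The middle column applies if either outcome suffices, the right-hand column if both are required.

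**4. Joint power if both are required.** Taking the printed blood-loss inputs at face value, power for blood loss is almost 1. Joint power is then practically the surgical-time power in step 2, for example 52% at 0.4 SD and 85% at 0.6 SD. It is governed by the outcome with no stated assumptions.

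**The case against.** The strongest reply is that the plan makes no false statement. It gives 85% as an input to a formula applied to three named variables, and no sentence says that this power covers both primary outcomes. That is correct: the defect is an omission.

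Several stronger readings are tempting and are not supported.

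- A reader might infer that the trial is underpowered for surgical time. With no SD or target difference, 0.60 SD cannot be turned into minutes or judged too large. Power is undocumented, and that is all that can be said.
- A reader might infer that the error rate is certainly inflated. It is inflated only if significance on either outcome is enough. If both must be significant there is no inflation. The document states neither rule.
- A reader might say that half of the primary objective is unpowered. Section 3 states an aim with lists of effectiveness and safety measures and does not divide it that way. The accurate statement is one of two primary outcomes.
- A reader might assume that blood loss at least is properly sized. Step 1 of the working shows that its 50 does not follow from its printed inputs.

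It is also fair to say that the bowel-recovery row does no harm to the planned size, since 24 is below 50, and that testing blood loss first is only one of several valid choices. Both points stand. None of this supplies the missing assumptions or the missing success rule.

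**Conclusion.** The point holds as an omission that should be corrected. For surgical time, one of two named primary outcomes, the stated 85% power is not established. At 50 per group it is reached only for a difference of about 0.60 SD or more, or about 0.66 SD if that outcome is tested at 2.5%. These thresholds depend only on the group size, alpha and power, and assume a comparison of means with no dropout.

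Followed as written, Section 6 does not guarantee the stated 5% error across the primaries. Under an either-suffices rule it is about 8.3% to 9.75% for correlations from 0.7 down to 0. Under a both-required rule the error is controlled, but joint power is unknown. The mismatch over bowel recovery time is a matter of consistency only.

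**What to change.** In Sections 4 and 6, state whether one or both primary outcomes must be significant, and control the error across them at two-sided 5%. Two suitable options if either may support a claim:

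- **Fixed sequence:** test blood loss first at 5%. Treat surgical time as confirmatory at 5% only if blood loss is significant; otherwise report it descriptively with a 95% CI.
- **Holm:** test the smaller p-value at 2.5% and, if significant, the other at 5%. This does not rank the outcomes.

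If both are required, say so; no adjustment is then needed.

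In the sample-size part of Section 2:

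- Add a line for surgical time stating that 50 per group gives 85% power for a difference of about 0.60 SD (about 0.66 SD at 2.5%). If the investigators have an SD, give the difference in minutes as well.
- Do not restate 85% power for blood loss until that row's inputs and n are reconciled. Check at the same time why the other two rows match 80% power.
- Remove the bowel-recovery row, or list bowel recovery time as a secondary outcome in Sections 2 and 4 if it is recorded.

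The cost is wording, plus the reconciliation of the table; these changes themselves need no extra patients. The downside is a conditional or somewhat weaker confirmatory claim on one primary outcome.

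### Section 2 ends the study at discharge while planning a day 3-4 examination, and Section 4 allows four weeks; unless reconciled, the follow-up window for secondary outcomes may depend on when a patient leaves

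*Combined protocol and SAP*

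**What the plan says.** Section 2 (Study design) makes four statements that bear on this point:

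- Outcomes: "Secondary outcomes include pain intensity, surgical complications, hospital stay, and pneumoperitoneum".
- Timing: "Blood loss and surgical time will be measured right after surgery while other outcomes will be measured during hospital stay".
- Visit: "Technically, the investigators will perform examination 3-4 days post-surgery".
- End of study: "Sampling will be stopped and the study will be concluded when patients are discharged from the hospital".

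Section 4 (Outcomes) repeats the list of secondary outcomes, names surgical site infection among the complications, and gives a different window: "the secondary outcomes will be evaluated within 4 weeks post-surgery by qualified practitioners".

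On conduct and analysis, Section 2 states "The study is a parallel-group randomized control trial with 2 arms and no blinding", and Section 5 (Populations and subgroups) says only "Populations: intention-to-treat".

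The plan does not define hospital stay (start, stop, units). It does not give an expected stay, the setting or content of the examination, the relation between examination and discharge, or a rule for missing values.

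**The concern.** Taken alone, Section 2 fits together only if every patient is still in hospital on day 3-4. For a patient ready to leave sooner it gives no instruction. Two things could then happen, and staff would know the arm in either case.

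- She leaves, and her participation ends before the examination. Complications that take time to appear, such as surgical site infection, are then looked for over a shorter period in patients who recover faster. If one arm recovers faster, that arm is observed for less time and may record fewer complications for that reason alone.
- She stays until the examination. Her recorded stay then partly reflects the study calendar, and differences between arms that arise before day 3 shrink.

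The Introduction gives quicker recovery as one advantage of single-port surgery, and hospital stay is the listed outcome that measures its duration. The safety comparison in Section 3 (Aims and objectives) includes complications. Both depend on which reading of the schedule is followed.

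**Working it through.** **1. The timing statements side by side**

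| Item | Section 2 | Section 4 |
|---|---|---|
| Primary outcomes | right after surgery | immediately after surgery |
| Secondary outcomes | during the stay | within 4 weeks of surgery |
| Examination | day 3-4, setting not given | not mentioned |
| End of data collection | discharge | not stated; the window implies up to 4 weeks |

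The primary outcomes agree. The secondary outcomes do not: for anyone discharged before four weeks, Section 2 stops observation while the Section 4 window is still open. No text says which governs.

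**2. What an early leaver would lose**

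- Blood loss and surgical time: nothing, as they are recorded at surgery.
- Hospital stay: nothing, as it is complete at discharge.
- Findings made at the examination or later: these are at risk under Section 2, but not under Section 4.

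**3. Size if discharge waits for the examination**

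The plan has no figure for length of stay, so there is nothing to reproduce. From the plan: 50 per arm (Section 2) and two-sided alpha of 0.05 (the formula uses z at 1 - α/2). Assumed: normally distributed stay, SD 1 day in each arm, true difference 0.5 day, and every patient kept until at least day 3.

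With μ the arm mean in days and c = (μ - 3)/1, the mean recorded stay is

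E[max(X, 3)] = 3 + φ(c) + c·Φ(c).

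- μ = 2: c = -1, so 3 + 0.2420 - 0.1587 = 3.083
- μ = 2.5: c = -0.5, so 3 + 0.3521 - 0.5 × 0.3085 = 3.198
- Recorded difference: 3.198 - 3.083 = 0.11 day, against a true 0.5 day

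Power is Φ(d / (s·√(2/50)) - 1.96), with d the recorded difference and s the root mean square of the two arm SDs. Without the floor: Φ(0.5/0.2 - 1.96) = 0.705. With it at means 2 and 2.5, the SDs shrink to 0.262 and 0.413, so s = 0.346 and power is Φ(0.1145/0.0691 - 1.96) = 0.38.

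| True means (days) | Share ready before day 3 | Recorded difference | Power with floor (0.705 without) |
|---|---|---|---|
| 2 vs 2.5 | 84% vs 69% | 0.11 | 0.38 |
| 2.5 vs 3 | 69% vs 50% | 0.20 | 0.51 |
| 3 vs 3.5 | 50% vs 31% | 0.30 | 0.61 |
| 4 vs 4.5 | 16% vs 7% | 0.45 | 0.69 |
| 5 vs 5.5 | 2% vs 1% | 0.49 | 0.705 |

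**4. Size if early leavers miss the examination**

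Under the same assumptions, the second column is the share unexamined. At 3 vs 3.5 days that is 25 of 50 against about 15 of 50. The faster arm has more missing examinations, and the missingness follows recovery.

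Loss of numbers alone, for an illustrative 0.6 SD difference in a continuous outcome taken at the examination, with power Φ(0.6/√(2/n) - 1.96):

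- n = 50 per arm: 0.85
- n = 40: 0.77
- n = 30: 0.64

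Selective loss could add bias to this. Its direction and size cannot be computed from the documents.

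**The case against.** A reader might infer that the schedule must do one of two things: impose a three-day minimum stay, or drop the fastest-recovering patients. The documents do not support that. The strongest case against it has five parts.

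- Section 2 is coherent if patients are normally in hospital on day 3-4, and its sequence (outcomes in hospital, examination, discharge) reads naturally that way. No expected stay is given, so early discharge is an assumption. This stands, and the point is conditional on it.
- Nothing makes discharge wait for the examination, so the floor is also an assumption. This stands.
- Section 4 allows assessment after discharge, so the examination of an early leaver need not be lost. This is true of Section 4, but it contradicts the end of study in Section 2. It shows that the sections need reconciling, not that the gap is closed.
- Early leavers keep their primary outcomes and their length of stay. The plan does not say what the examination records, so a missed examination is not necessarily a missing outcome. This stands and limits the point to secondary outcomes whose observation would continue to day 3-4 or later.
- The plan does not say who decides discharge or by what criteria. Absence of blinding therefore makes influence by knowledge of the arm possible; it does not show that it occurs.

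The calculation supports the same caution: with mean stays of 5 and 5.5 days there is practically no effect.

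**Conclusion.** The point holds as a contradiction with a conditional consequence. Section 2 stops observation at discharge; Section 4 keeps the secondary outcomes open for up to four weeks. If Section 2 is followed and some patients are ready to leave before day 3, either their ascertainment window depends on recovery and possibly on arm, or hospital stay is compressed by the visit.

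Under the stated assumptions, compression ranges from almost nothing at mean stays of 5 and 5.5 days to loss of about three quarters of a 0.5-day difference at 2 and 2.5 days (0.11 of 0.5 recorded). Where the trial falls in that range depends on the usual stay, which the documents do not give. The primary outcomes are unaffected. This should be corrected because correction is cheap; it does not undermine the trial's main comparison.

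**What to change.** Reconcile the examination and end-of-study sentences in Section 2 with the four-week sentence in Section 4, so that:

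1. Data collection does not stop at discharge.
2. Secondary outcomes other than length of stay are assessed over the same fixed post-surgery window in every patient in both arms, with the planned examination at the same time point whether or not the patient has left.
3. Hospital stay is recorded as actual time from end of surgery to discharge.
4. The protocol states whether the study examination bears on discharge.

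Actual time to discharge is preferable here to a judgement of readiness to leave, which would be more subjective in an unblinded trial. No discharge rule is proposed.

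The cost is a few sentences and a discharge date and time on the case report form. The downside is that some patients discharged early would return once for an examination already planned.

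### The blood-loss row that sets the trial size does not reproduce: the printed formula and inputs give 8 per group, not 50, and the other two rows match 80% power rather than the stated 85%.

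*Combined protocol and SAP*

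**What the plan says.** Section 2 (Sample size calculation) prints the usual formula for comparing two means, with the normal quantile at 1 − α/2, alpha 0.05 and beta 0.15, that is "statistical power = 0,85". It defines n as a per-group minimum. Randomization uses "computer-generated sequences with allocation ratio 1:1".

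The table takes its inputs from the one cited study and gives three sizes:

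- "Bowel recovery time": 24
- blood loss: 50
- visual analogue scale (VAS): 14

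The calculation closes with: "The investigators anticipate to obtain the sample size of 50 for each group". Section 4 says: "The primary outcomes of interest are the amount of blood loss during surgery, and surgical time". Surgical time has no row in the table, and bowel recovery is not among the outcomes listed in section 4.

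**The concern.** The blood-loss row has a gap of 210 between means and SDs of 156.9 and 104. The gap exceeds either SD, so this is a large standardized effect and a small sample should be enough. A requirement of 50 per group does not fit those inputs. Bowel recovery has a smaller gap relative to its SDs (1.0 against 1 and 1.4), yet it is said to need only 24.

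This row fixes the trial size and is the only link between that size and a primary outcome. If it fails, the 50 has no valid derivation for blood loss. If a mean or SD was copied wrongly, nobody can tell from the document what power the trial has for the correct values. A separate question is whether the stated 85% is the power that was actually used.

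**Working it through.** **Inputs** (all from section 2): two-sided alpha 0.05; power 0.85; r = 1; means and SDs as tabulated.

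**Formula** (as printed, r = 1): n = (z₁₋α/₂ + z₁₋β)² × (σ₁² + σ₂²) / Δ². The squared multiplier is 7.849 at 80% power, 8.978 at 85% and 18.372 at 99%.

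**Rows where the plan's figure can be reproduced**

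- Bowel recovery: (1² + 1.4²)/1.0² = 2.96. At 80%, 2.96 × 7.849 = 23.23, so **24**, as printed. At 85%, 2.96 × 8.978 = 26.58, so 27.
- VAS: (0.5² + 0.6²)/0.6² = 1.694. At 80%, 13.30, so **14**, as printed. At 85%, 15.21, so 16.

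By the same formula, n = 24 and n = 14 give 81.3% and 82.0% power.

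**Blood loss**

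(156.9² + 104²)/210² = 35433.6/44100 = 0.8035.

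- 80%: 6.31, so 7
- 85%: 7.21, so **8**, against 50 printed
- 99%: 14.76, so 15

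| Row | Printed | At 80% | At 85% (stated) |
|---|---|---|---|
| Bowel recovery | 24 | 24 | 27 |
| Blood loss | 50 | 7 | 8 |
| VAS | 14 | 14 | 16 |

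**Could another method give 50 for blood loss?** At 85% power:

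- one-sided alpha 0.05: 6
- noncentral t: 9
- alpha split to 0.025 for two primary outcomes: 9
- allowance for Mann-Whitney efficiency (0.955 or 0.864): 8 or 9
- total of both arms instead of per group: 16

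None comes near 50, and the document states no allowance for dropout or multiplicity.

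**What would give 50?** Changing one quantity at a time:

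- gap between means: √(8.978 × 35433.6/50) = 79.8 at 85%, or 74.6 at 80%, instead of 210
- 4-port SD: about 485 (85%) or 520 (80%), instead of 156.9
- 1-port SD: about 470 (85%) or 506 (80%), instead of 104

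A tenfold decimal slip in the 1-port mean (33.5) gives 38 at 85% or 34 at 80%. In the 1-port SD (1040) it gives 226 or 197. Neither restores 50.

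**What 50 per group gives on the printed inputs.** SE = √(35433.6/50) = 26.62 and 210/26.62 = 7.89. Then 7.89 − 1.96 = 5.93, so power is over 99.99%.

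**The case against.** The strongest reply is that the error is harmless. On the printed figures 50 per group exceeds what every row needs, so the mistake runs toward more patients and changes nothing in enrolment or conduct. That is right as far as it goes, and underpowering is not claimed. But the reassurance rests on the inputs of the very row that fails, and it does not cover surgical time, which has no row.

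A second reply is that one digit was probably miscopied or lost. A gap of 75 with the printed SDs gives 7.849 × 35433.6/75² = 49.4, so 50, at 80% power, the level at which the other rows match. One wrong mean and one misstated power would then explain the whole table. This is plausible but cannot be settled without the cited study. It also means that 8 is a consistency check, not a proposed trial size.

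Third, the power mismatch is small: three patients per group for bowel recovery and two for VAS, in rows that do not set the size. That is fair; it is secondary to the blood-loss row. Still, both rows match exactly at 80%, and a one-sided reading at 85% gives 22 and 13, which neither matches nor agrees with the printed 1 − α/2.

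Finally, the table heads its comparator column four-port, whereas the cited title reads "Comparison of single-port and three-port laparoscopic salpingectomy in the management for tubal pregnancy". This proves no numerical error, but it is a further reason to check the transcription.

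**Conclusion.** The concern holds. The blood-loss row is about six times what its own formula and inputs give: 50 against 8 at the stated 85% power, or 7 at 80%. No standard variant and no stated inflation closes the gap. At 85% none of the three rows reproduces; at 80% two do exactly.

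The document cannot show which blood-loss figure is wrong, or whether the stated power or the 24 and 14 should change. If the inputs are right, 50 per group is far more than that row requires. If they are not, the power for blood loss is unknown. On the printed inputs the largest row would be bowel recovery, at 27 per group (54 in total) at 85% or 24 (48 in total) at 80%, and that is not a listed outcome.

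These results assume the printed formula, two-sided alpha 0.05 and equal allocation.

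**What to change.** 1. Check the blood-loss means and SDs, and the number of ports in the comparator heading, against the cited study, and correct the row.
2. State one power value and recompute all three rows with it. On the printed inputs, in table order, these are 24, 7 and 14 at 80%, or 27, 8 and 16 at 85%.
3. If the blood-loss inputs change, state the power that 50 per group gives with the corrected values.
4. If they are confirmed, keep 50 per group, say that it exceeds the calculated minimum, and state what it can detect: with SDs 156.9 and 104, a mean difference of about 80 at 85% power or about 75 at 80%. Add that this depends on those SDs and on a comparison of means. Section 6 sends non-normal data to the Mann-Whitney test, for which the figure is only a guide.

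The cost is one check of the source and a change of wording in section 2. Enrolment is unchanged.

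### Beta-hCG is named as an effectiveness measure without a time point or metric, and the plan has only unadjusted tests; comparing post-operative levels this way would be unbiased but could lose much of the power.

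*Combined protocol and SAP*

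**What the plan says.** Section 3 (Aims and objectives) says that "the surgical effectiveness will be evaluated via beta-hCG values, ultrasound imaging, and rate of switching to open surgery". Beta-hCG is the only laboratory measure of effectiveness. The section does not say when the sample is taken, on what scale it is analysed, or whether it is compared with a pre-operative value.

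Section 4 (Outcomes) lists beta-hCG nowhere. It says "The primary outcomes of interest are the amount of blood loss during surgery, and surgical time", and then "Secondary outcomes include pain intensity as indicated by visual analogue scale, surgical complications such as organ damages and surgical site infections, hospital stay, and pneumoperitoneum".

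Section 6 (Analyses) covers continuous variables in one sentence: "T-test for normally distributed continuous variables and Mann-Whitney-U test for non-normally distributed continuous variables will be used to compare between groups". No covariate, change score or transformation appears anywhere in the plan.

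On allocation, Section 2 (Study design) says "All patients are randomized using computer-generated sequences with allocation ratio 1:1". On timing, it says "Technically, the investigators will perform examination 3-4 days post-surgery", without naming hCG as part of that examination, and that "the study will be concluded when patients are discharged from the hospital". Section 4 instead has the secondary outcomes assessed over the four weeks after surgery.

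**The concern.** Take as a working premise that hCG falls after surgery as a fraction of its starting value. A post-operative level is then the pre-operative level multiplied by the fraction remaining, and only that fraction bears on the operation. The eligibility criteria in Section 2 set no limit on hCG or gestational age, and the description of randomisation mentions no stratification, so nothing in the plan narrows the pre-operative spread.

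If levels are compared without adjustment, that spread goes into the error term. A real difference in clearance could then be missed, and the non-significant result could be read as equal effectiveness. Because the metric is open in an unblinded trial, the choice between level, change and percentage fall could also be made after the data are seen.

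**Working it through.** **Plan's own figure.** There is none for beta-hCG. The 50 per group in Section 2 is the figure on the blood loss row of the sample size table. It is taken here as the number of patients available.

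**Inputs from the documents.** n = 50 per arm; two-sided α = 0.05 (the formula in Section 2 uses z at 1−α/2).

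**Assumptions (the documents give no hCG mean, SD or correlation).** On the natural-log scale, post = pre + log clearance, with clearance independent of the pre-operative value. The SD of log clearance is sc = 0.5. The SD of log pre-operative hCG is sb = 0.5, 1.0 or 1.5. The true difference in clearance is δ = 0.3 log units, a ratio of exp(0.3) = 1.35.

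**Formulas.**
- Unadjusted: SE = √(sb² + sc²) × √(2/50).
- Adjusted for baseline: SE ≈ sc × √(2/50) = 0.5 × 0.2 = 0.10.
- Approximate power = Φ(δ/SE − 1.96).

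**By formula.**
- sb = 0.5: SE = √0.50 × 0.2 = 0.141; δ/SE = 2.12; power ≈ Φ(0.16) = 56%.
- sb = 1.0: SE = √1.25 × 0.2 = 0.224; δ/SE = 1.34; power ≈ Φ(−0.62) = 27%.
- sb = 1.5: SE = √2.50 × 0.2 = 0.316; δ/SE = 0.95; power ≈ Φ(−1.01) = 16%.
- Adjusted, any sb: δ/SE = 3.0; power ≈ Φ(1.04) = 85%.

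The unadjusted variance is (sb² + sc²)/sc² = 2, 5 and 10 times the adjusted variance.

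**By simulation (3,000 trials per setting, δ = 0.3).**

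| sb | Pre/post correlation | t-test on log level | Mann-Whitney on level | Change in log | ANCOVA |
|---|---|---|---|---|---|
| 0.5 | 0.71 | 55% | 53% | 84% | 84% |
| 1.0 | 0.89 | 27% | 26% | 85% | 85% |
| 1.5 | 0.95 | 16% | 15% | 85% | 85% |

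**Validity of the unadjusted comparison.** With δ = 0, the two unadjusted tests rejected in 4.6-5.2% of trials. Across all settings, the bias of the log-scale arm difference was at most 0.004. The cost is therefore in precision.

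**If the pre/post correlation is weaker.** ANCOVA multiplies the variance by 1 − ρ². With 50 per arm and 85% power, the unadjusted comparison detects (1.96 + 1.036) × √(2/50) = 0.60 SD. Multiplying by √(1 − ρ²) gives 0.57, 0.52, 0.43 and 0.26 SD at ρ = 0.3, 0.5, 0.7 and 0.9. For a true difference of 0.4 SD, power is 52% unadjusted, against 55%, 64%, 80% and over 99% adjusted. The gain is small at ρ = 0.3 and large at ρ = 0.7 or more.

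**The case against.** The strongest reply is that the plan does not commit to this analysis. Section 3 says only that beta-hCG values will be used; the plural fits serial or paired measurements, and a percentage fall or log ratio could go into the same t-test or Mann-Whitney test. Beta-hCG is in neither outcome list, so no test is assigned to it. This stands: comparing unadjusted levels is the literal reading, not a stated rule, so the loss of power is conditional on that reading. The metric still needs to be written down.

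A reader might also infer that the result would reflect pre-operative hCG and not clearance. The documents do not support that. Allocation is randomised 1:1, so pre-operative hCG is balanced in expectation and the log-scale arm difference estimates the clearance difference without bias. One patient's level can mislead about that patient's clearance, but this does not carry over to a bias in the arm comparison.

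Nor does chance imbalance add false positives. With an assumed pre-operative log SD of 1.0 to 1.6, baseline variation alone gives a geometric-mean ratio of up to exp(1.96 × SD × √(2/50)) = 1.48 to 1.87 at the edge of its 95% range. The unadjusted standard error already contains that variation.

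Finally, it is tempting to read the Section 2 examination 3-4 days after surgery as the hCG time point. The documents do not say that hCG is drawn then, or that a pre-operative value is recorded for the study.

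**Conclusion.** The point holds as one of definition and efficiency. An effectiveness measure has no stated time or metric, and the only tests on offer ignore baseline. If post-operative levels are compared with those tests, the comparison is valid but imprecise. Under the assumptions above, power drops from about 84-85% to between 55% and 16%, depending on the pre-operative spread. These figures rest on assumed SDs, on a proportional fall independent of baseline and on a difference of 0.3 log units, none of which the documents supply. With a weak pre/post correlation the loss is slight. Beta-hCG is neither a primary outcome nor the basis of the sample size, so this is a worthwhile improvement and not the repair of an invalid analysis.

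**What to change.** In Sections 3 and 6, replace the general reference to beta-hCG values with a defined analysis:

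- Analyse log post-operative beta-hCG at one stated sampling time, with log pre-operative beta-hCG as covariate (ANCOVA).
- Report the adjusted ratio between arms with its 95% CI.
- Summarise the percentage fall from the pre-operative value descriptively, by arm.
- Record the date and time of both samples.

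Reconcile the end of follow-up beforehand (discharge in Section 2, four weeks in Section 4), because it decides which post-operative samples can exist. Then choose the sampling time from samples already taken. Beta-hCG's absence from the Section 4 lists is a separate gap; listing it there would not by itself settle the metric or the analysis.

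**Cost.** If both values are on record, this is a few sentences of plan text and one covariate in a Stata model. It depends on a pre-operative value being available, and needs a short rule for missing baselines and for results below the assay limit, since logs are taken. If no post-operative hCG is being collected at a common time, the cost becomes one of data collection; the documents do not show whether that is so.
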